7.2.4 Targeted Screening Arm (Current Process – Control)

Students randomized to the targeted screening arm will complete their routine school-based screenings. Students will be followed through the academic year for SAP triage intakes initiated by the standard pathway (concern by teachers, nurse, parent, peer, or self-referral), any referrals and treatment engagement.

7.2.5 Sharing Screening Results

At 14 years of age, PA youth are eligible to consent to mental health services without parental consent, therefore, screening results will not be shared with parents. Those students with scores ≥ 11 (MDD screen positive) corresponding to moderate depressive symptoms will, however, proceed through the standard process for anyone referred by traditional means to a SAP triage interview. The student will either refer to appropriate community or school-based treatment or therapy (MDD identified) or SAP will determine no follow-up is needed. For those who are recommended to additional services by SAP, treatment engagement will be tracked per current SAP process. As per current school policy, students with suicidal feelings will receive immediate referral to emergency care and parents will be notified by the school.

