1.2 Primary Study Endpoints

MDD composite which includes MDD screen positive for the universal screening arm (or concern in the targeted screening group), MDD identification, and MDD treatment engagement. Each of the primary study endpoints will be collected at the individual level by the school district by the end of the school year. No identifiable information will be collected by study staff.

Universal Group

- 1) Adolescents with PHQ-9 score ≥ 11 (screen Sept-March of the school year) or who at any point in the year exhibit behavior concerning for MDD prompting a SAP triage request, 2) Adolescents identified with MDD by SAP triage, and 3) Adolescents who successfully engage with at least one SAP recommendation

Targeted Group

1) Adolescents with behavior concerning for MDD prompting a SAP triage request, 2) Adolescents identified with MDD by SAP triage, and 3) Adolescents who successfully engage with at least one SAP recommendation

Concern for MDD based on a primary or secondary potentially MDD related SAP "incoming referral reason"

SAP triage is not diagnostic, so MDD identified based on recommendations for MDD related school or community services (e.g. mental health treatment services)

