1.3 Secondary Study Endpoints

The secondary endpoints listed below are individual level data points that will be obtained from the school district and/or SAP. No identifiable information will be collected by study staff.

MDD screen positive or MDD concern prompting Student Assistance Program triage

Universal screening arm: Adolescents who have a PHQ-9 score ≥ 11 (screening with the PHQ-9 is planned for September to March) or who at any point in the school year exhibit behavior concerning for MDD which prompts self or collateral request for SAP triage.

Targeted screening arm: Adolescents with behavior concerning for MDD which prompts self or collateral request for SAP triage at any point during the school year.

Suicidal adolescent (includes suicidal thoughts [positive response to PHQ-9 item 9], attempts and completed)

Universal screening arm: Patient health questionnaire positive response to question #9 re: suicidal thoughts, which requires management by the state-mandated school crisis plan or student self or collateral report of suicidal thoughts, which requires management by the state-mandated school crisis plan (source school district).

Targeted screening arm: Student self or collateral report of suicidal thoughts, which requires management by the state-mandated school crisis plan (source school district).

Any student suicide attempts or completed suicides shared with the school district will also be included.

MDD identification

Universal and targeted screening arms: Adolescents who are identified as having MDD based on triage by the school SAP team. As SAP triage is not diagnostic, MDD identified will be based on SAP recommendations for school or community services which are MDD related (e.g. mental health treatment services).

MDD treatment engagement

Universal and targeted screening arms: Adolescents who successfully engage with at least one SAP recommendation. This may be fulfilled by parental report that an appointment was successfully scheduled

The secondary endpoints listed below are aggregate data points by grade level that will be obtained from the school district and/or SAP. No identifiable information will be collected by study staff. Please

note, secondary outcomes may no longer be available due to COVID-19 school closures and cancellation of state standardized testing.

Standardized test scores (i.e. Keystone exams, PSAT, SAT/ACT)
Student school policy violations and/or suspensions
Missed school days
Grade point averages

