At the time of the actual universal screening students will also be provided the chance to opt out by clicking the appropriate opt out box on the iPad handed to them. We anticipate this will lead to study enrollment of 80% of eligible students. The first screen will describe PHQ-9 and that proceeding is voluntary. The completion of the PHQ-9 implies a student's voluntary consent to participate in the research. Unless the parent opt out is returned, participants in both arms will be followed through the school year for SAP triage, follow-up referrals and treatment engagement. Those students in the universal screening arm with PHQ-9 scores ≥ 11 (MDD screen positive) corresponding to moderate depressive symptoms, will proceed through the standard process for anyone referred by traditional means to a SAP triage interview. The student will either be referred to appropriate community or

school-based treatment or SAP will determine no follow-up is needed. For those who are recommended to additional services by SAP, treatment engagement will be tracked per current SAP processes. The study team will receive individual level outcome data from the school district, containing no identifiable information.

Additionally, we will recruit 1-2 school staff members to participate in our feedback guide interview upon completion of the screener/screening process year. We are not collecting any PHI, nor will names of the school staff participants be disclosed in the use of manuscripts/ written publications. Staff members from two schools were recruited and completed the Final Feedback Guide interview [REDACTED] as a pilot to ensure the final version of the Feedback Guide was thorough and comprehensive.

To better understand the long-term feasibility of the screening process, school contacts who participated in the first year of screening will be asked to participate in a Year 2 feedback guide interview. This guide will provide information about the screening process impacts and sustainability in [REDACTED] high schools. The remaining schools who participated in screenings during the 2019-2020 school year, will participate in the Year 2 feedback guide interview at the end of the 2020-2021 school year.

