Additional secondary outcomes will include MDD screen results, MDD concern prompting Student Assistance Program triage, MDD identification and MDD treatment engagement analyzed individually (rather than as part of MDD composite). Finally any suicidal adolescents (suicidal thoughts [positive response to PHQ-9 item 9], attempts and completed) will be analyzed as a secondary outcome.

We need to collect data for individuals for 3 main reasons. First, we expect approximately 20% of students to opt out from the study, with opt out rates varying by grade. Aggregate data would necessarily include outcomes for students who are not enrolled in the study. This is particularly problematic for the universal screening group because students who opt out will not be offered the depression screening tool (PHQ-9). Second, we need to obtain gender and race/ethnicity to conduct important planned secondary analyses (subgroup analyses) that will examine efficacy of universal screening by these groups. In particular, we expect that females and minority students will have much higher rates of major depression disorder identified in the universal screening group. Third, in the

universal screening group, we will be able to link responses to the PHQ-9 to outcomes, which will allow for estimation of important measures such as the false positive rate of the PHQ-9 (score ≥ 11 , but SAP process determines no further referrals are needed). These measures will inform decision-making regarding the potential for implementation of the intervention (in other schools) should the results of the trial ultimately show efficacy.

Efforts will be made to ensure completeness of data where possible, but missing data will occur for a number of anticipated reasons. First, a student may move during the course of the school year to another school district or drop out from school entirely. No data will be collected after this time point. Second, parents may opt out their child from the study at any time during the school year. Third, students who turn 18 during the school may decide to opt out of the study themselves. In both of these instances, data from SAP referrals that occur after opting out will not be collected for purposes of the study. Fourth, during the one-time universal screening phase, students may decide to leave data forms incomplete, including the PHQ-9. To decrease these instances, the PHQ-9 will be taken on an iPad program and the survey will alert if the form is left incomplete.

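### The PHQ-9 false-positive rule and the 7.2.5 label split screen positives into referred or not referred, while 1.2 and 1.3 require an MDD-related recommendation, so the false-positive figure can be understated

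*Combined protocol and SAP*

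**What the plan says.** SAP here means the Student Assistance Program. All references are to the current protocol version (14 schools).

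- **1.2 Primary Study Endpoints.** After listing the three steps of the composite for each arm, the section gives "SAP triage is not diagnostic, so MDD identified based on recommendations for MDD related school or community services (e.g. mental health treatment services" as the one criterion for step 2.
- **1.3 Secondary Study Endpoints.** The separate endpoint of MDD identification covers both arms ("Universal and targeted screening arms: Adolescents who are identified as having MDD based on triage by the school SAP team"), with the same criterion: "MDD identified will be based on SAP recommendations for school or community services which are MDD related (e.g. mental health treatment services".
- **7.2.5 Sharing Screening Results.** Students scoring 11 or more "proceed through the standard process for anyone referred by traditional means to a SAP triage interview". Then: "The student will either refer to appropriate community or school-based treatment or therapy (MDD identified) or SAP will determine no follow-up is needed". The words MDD related do not appear, and no third result is provided for.
- **7.2.1 Enrollment.** The same flow is described without the identification label; the alternatives are referral to community or "school-based treatment or SAP will determine no follow-up is needed".
- **8.3 Statistical methods, and the closing paragraph of 1.3.** A PHQ-9 false positive is a score of 11 or more "but SAP process determines no further referrals are needed".

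The 8.3 description of the composite repeats the three steps. It neither restates the step 2 criterion nor says which section governs its coding.

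**The concern.** Two rules are in use for what counts as a confirmed screen. Under 1.2 and 1.3 it is the type of recommendation that matters. Under the false-positive rule, and on a literal reading of the 7.2.5 parenthesis, any referral is enough. The rules disagree about one kind of student: the screen positive whom SAP refers only for a problem unrelated to MDD.

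Two things are at stake. The first is the PHQ-9 false-positive figure, which 1.3 and 8.3 say will inform decisions about using the screen in other schools. The second is step 2 of the primary composite, which could be coded differently by two analysts who started from different sections. The later steps would not correct this. Step 3 accepts engagement with any one SAP recommendation, and a PHQ-9 score of 11 or more satisfies step 1 by itself. For a student entering through the PHQ-9, step 2 is the only MDD filter after the questionnaire.

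**Working it through.** **1. The plan's own figure.** Section 8.1 gives (3,900 + 8,150) × 0.80 = 9,640 students, or 4,820 per group. For 3% v 6%, the standard error of the difference is √[(0.03×0.97 + 0.06×0.94)/4,820] = 0.0042. Then 0.03/0.0042 − 1.96 is about 5.2, so power exceeds 99%, as 8.2 states. With 15% attrition (4,820 × 0.85 = 4,097 per group) it still does. Clustering is ignored because no intraclass correlation is given. No stated figure depends on the wording of 7.2.5.

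**2. The rules side by side, for a student with PHQ-9 ≥ 11.**

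| SAP triage result | MDD identified (1.2, 1.3) | Literal 7.2.5 label | False positive (1.3, 8.3) |
|---|---|---|---|
| MDD-related recommendation | Yes | Yes | No |
| Other recommendation only | **No** | Yes, if read as any referral | **No** |
| No follow-up | No | No | Yes |

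The middle row is the inconsistency: neither identified nor a false positive.

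**3. Size for the false-positive figure.** Take as denominator the screen positives who complete triage (an assumption; the plan names no denominator). Let a, b and c be the shares in the three rows, with a + b + c = 1.

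- Rule as written: c.
- Rule consistent with 1.2 and 1.3: 1 − a = b + c.
- Understatement: b = q(1 − c), where q = b/(a + b) is the share of referrals that are not MDD related.

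Neither q nor c is in the documents. Assuming q = 5%, 10% or 20%, the understatement is at most 5, 10 or 20 percentage points (c near zero). If half of screen positives are referred (c = 50%), it is 2.5, 5 or 10 points. It is zero only if no screen positive receives a non-MDD referral alone.

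**4. Primary comparison, only if coders used 7.2.5 for PHQ-9 positives.** This is an illustration, not an estimate. Take 3% v 6% as the rates under 1.2 and 1.3, 4,097 per group, and equal engagement whatever the referral type. The planned odds ratio is (0.06/0.94)/(0.03/0.97) = 2.06. The standard error of its logarithm is √[1/(4,097×0.03×0.97) + 1/(4,097×0.06×0.94)] = 0.113. Section 1.2 also admits universal-arm students through behaviour-prompted SAP requests, so let h be the share of universal-arm events that arise through the PHQ-9. The loosely coded rate is u = 0.06 × [(1 − h) + h/(1 − q)].

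| q | u (h = ½) | OR (h = ½) | Shift in SE (h = ½) | OR (h = 1, upper case) | Shift in SE (h = 1) |
|---|---|---|---|---|---|
| 5% | 6.16% | 2.12 | 0.25 | 2.18 | 0.48 |
| 10% | 6.33% | 2.19 | 0.51 | 2.31 | 1.00 |
| 20% | 6.75% | 2.34 | 1.12 | 2.62 | 2.12 |

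Both q and h are assumed. The table also supposes complete use of 7.2.5 for PHQ-9 positives and of 1.2/1.3 for everyone else.

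**The case against.** A reader might infer that the plan scores step 2 more loosely in the universal arm only, since PHQ-9 positives exist only there, and so inflates the primary odds ratio. The documents do not support that. Section 1.3 applies its definition expressly to both arms, and 1.2 states its criterion once for both. Section 7.2.5 is a procedural section on sharing results, and it sends screen positives through the same triage as everyone else. Nothing directs coders to it for endpoint scoring.

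The parenthesis can also be read as shorthand. It speaks of appropriate treatment or therapy after a positive depression screen, close to the example of mental health treatment services in 1.2 and 1.3. The sentence is identical in the protocol version for eight schools, whose endpoint sections contain no criterion for identification. It appears to have been carried forward when the criterion was added. On this view 1.2 and 1.3 are the natural authority. All of this stands, and it confines the primary-endpoint issue to a risk of misreading.

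It does not dispose of the false-positive rule. That rule turns on whether SAP finds "SAP process determines no further referrals are needed", which is wider than treatment or therapy and cannot be read as shorthand for MDD-related services. It is fair to add that the measure is estimated in one arm, is not a listed endpoint and enters no between-arm comparison. That limits the consequence without removing the inconsistency. Non-MDD referrals are also not fanciful: 1.2 finds it necessary to restrict both incoming reasons and recommendations to MDD-related ones.

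**Conclusion.** The concern holds in a narrow form. As written, the false-positive rule disagrees with the trial's own definition of MDD identification and understates the false-positive share by b, the share of screen positives with only a non-MDD referral. The direction is certain whenever such referrals occur. The amount is not derivable from the documents; under the assumed q of 5% to 20% it is at most 5 to 20 percentage points.

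For the primary comparison there is an unaligned label, not a demonstrated bias. Any effect requires coders to prefer 7.2.5 to 1.2 and 1.3, and its size rests entirely on undocumented values of q and h. The stated power is unaffected.

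**What to change.** 1. In 7.2.5, reword the parenthesis so that identification applies only when SAP recommends an MDD-related school or community service, as in 1.2 and 1.3.
2. In 8.3, state that step 2 of the composite, and the separate identification endpoint, are coded from that criterion in both arms, whatever the route into SAP.
3. In 1.3 and 8.3, report students with PHQ-9 ≥ 11 in three categories: MDD-related recommendation, other recommendation only, and no follow-up. Count only the first as a confirmed positive.

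The cost is wording. The type of recommendation is already needed to apply 1.2 and 1.3, so no new data are required. The one downside is that the reported false-positive figure may be somewhat less favourable to the screen.

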7.3 Duration of Participation

The student’s participation is limited to the 5 minutes it takes for them to participate in the screening process.

The school staff members who participate in the feedback guide interview is limited to the 45 minutes it takes for them to complete it.

8.0 Subject Numbers and Statistical Plan

8.1 Number of Subjects

The 9 HRSA funded schools to be included in the study have an estimated total enrollment of approximately 3,900 students (the PCORI funded urban schools have a total enrollment of approximately 8,150 students). The overall rate of parental opt out is expected to be around 20%,

resulting in approximately 9,640 students included in the study. We assumed a 15% attrition rate for students who move, drop out of school, or opt out later in the school year. This number will be finalized once we have a final confirmed list of participating schools. However, as the total number of students is greater than that originally projected below, the sample size determination section will be unchanged.

8.2 Sample size determination

A total of 4,820 (estimated) students in each randomized group (an overall sample size of 9,640 [estimated]) yields >99% statistical power to detect a difference of 3% versus 6% using a 2-sided test conducted at a Type I error rate of 5% in a mixed effect logistic regression model.

8.3 Statistical methods

The principles of intention-to-treat (ITT) will be used for all statistical analyses related to primary and secondary aims. For the primary aim comparing universal to targeted screening, the statistical analysis will be conducted using a mixed effects logistic regression model. The primary outcome, MDD composite, will be an indicator whether a student was screen positive (or concerns raised in the targeted screening arm), identified as having MDD and subsequently engaged in treatment (1=yes, 0=no). The model will include a fixed effect for randomized group (0=targeted screening, 1=universal screening) and a random effect for school. The random effect accounts for correlation among students enrolled within the same school. The primary parameter of interest will be the log odds of MDD composite in the universal screening group compared to the targeted screening group. Statistical significance of the log odds will be assessed using a 2-sided Wald test. Point estimates for the odds ratio along with a 95% confidence interval will be reported.

For the analysis of Hypotheses 2 and 3 (Objective 1) evaluating universal screening and targeted screening by selected subgroups, the same mixed effects logistic regression modeling framework will be used, but the model will be extended by including a fixed effect for subgroup and an interaction effect for subgroup by randomized group. The interaction term will be the parameter of interest. A significant interaction term indicates that rates of MDD treatment engagement for universal versus targeted screening differ by subgroup level (e.g. female vs. male). For the secondary analyses (Objective 2) that evaluates universal screening and targeted screening based on school SAP data, we will have only 64 total data points (4 grades in each of the 14 schools). Mixed-effects linear (continuous outcomes) and logistic regression (binary outcomes) will be used, as appropriate, with a fixed effect for randomized group and a random effect for school. The parameter of interest will be the log odds for the universal compared to the targeted screening group. Due to the smaller sample size used for these outcomes, these analyses will be considered to be primarily hypothesis-generating. Potential mediating variables (socioeconomic status, ratio of guidance counselors to students and availability of school-based mental health services) will be evaluated for both the Objective 1 and 2 hypotheses.

Additional secondary outcomes will include MDD screen results, MDD concern prompting Student Assistance Program triage, MDD identification and MDD treatment engagement analyzed individually (rather than as part of MDD composite). Finally any suicidal adolescents (suicidal thoughts [positive response to PHQ-9 item 9], attempts and completed) will be analyzed as a secondary outcome.

We need to collect data for individuals for 3 main reasons. First, we expect approximately 20% of students to opt out from the study, with opt out rates varying by grade. Aggregate data would necessarily include outcomes for students who are not enrolled in the study. This is particularly problematic for the universal screening group because students who opt out will not be offered the depression screening tool (PHQ-9). Second, we need to obtain gender and race/ethnicity to conduct important planned secondary analyses (subgroup analyses) that will examine efficacy of universal screening by these groups. In particular, we expect that females and minority students will have much higher rates of major depression disorder identified in the universal screening group. Third, in the

universal screening group, we will be able to link responses to the PHQ-9 to outcomes, which will allow for estimation of important measures such as the false positive rate of the PHQ-9 (score ≥ 11 , but SAP process determines no further referrals are needed). These measures will inform decision-making regarding the potential for implementation of the intervention (in other schools) should the results of the trial ultimately show efficacy.

Efforts will be made to ensure completeness of data where possible, but missing data will occur for a number of anticipated reasons. First, a student may move during the course of the school year to another school district or drop out from school entirely. No data will be collected after this time point. Second, parents may opt out their child from the study at any time during the school year. Third, students who turn 18 during the school may decide to opt out of the study themselves. In both of these instances, data from SAP referrals that occur after opting out will not be collected for purposes of the study. Fourth, during the one-time universal screening phase, students may decide to leave data forms incomplete, including the PHQ-9. To decrease these instances, the PHQ-9 will be taken on an iPad program and the survey will alert if the form is left incomplete.

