8.3 Statistical methods

The principles of intention-to-treat (ITT) will be used for all statistical analyses related to primary and secondary aims. For the primary aim comparing universal to targeted screening, the statistical analysis will be conducted using a mixed effects logistic regression model. The primary outcome, MDD composite, will be an indicator whether a student was screen positive (or concerns raised in the targeted screening arm), identified as having MDD and subsequently engaged in treatment (1=yes, 0=no). The model will include a fixed effect for randomized group (0=targeted screening, 1=universal screening) and a random effect for school. The random effect accounts for correlation among students enrolled within the same school. The primary parameter of interest will be the log odds of MDD composite in the universal screening group compared to the targeted screening group. Statistical significance of the log odds will be assessed using a 2-sided Wald test. Point estimates for the odds ratio along with a 95% confidence interval will be reported.

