5.3.3.2 Assent of subjects who are not yet adults

Students in the universal arm will have the option to decline participation themselves on the screening day via the iPad handed to them. The first screen will describe PHQ-9; inform students that participation is voluntary; and participation may be stopped at any time and will not affect their school standing. The completion of the PHQ-9 implies a student's voluntary consent to participate in the research. Students who decide not to participate will not complete the PHQ-9, but will still be tracked similar to students randomized to the targeted screening arm. The study team will obtain their demographic information and the student will be followed through the academic year for SAP triage intakes initiated by the standard pathway (concern by teachers, nurse, parent, peer, or self-referral), any referrals and treatment engagement. No identifiable information will be obtained and it will be noted in study records that the student did not assent to participate in the MDD screener. A copy of this assent form is included in the consent form section.

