7.0 Study Design and Procedures

7.1 Study Design

Due to the timeline for this funding opportunity, with an anticipated July 2018 start, 3 schools will engage in the randomized control trial (RCT) in study year 1 and the additional 13 schools in study year 2. Many large scale randomized control trials do not enroll all participants at one time point, and in many cases enrollment occurs slowly over the course of several years. We do not anticipate there will be major changes over the course of two academic years that would significantly alter the results compared to conducting the RCT in the same academic year, especially because students will be randomized within schools. Finally, staggering enrollment will give the research team the opportunity to troubleshoot any unanticipated issues with the first 3 participating schools. The intervention ended early in study year 2 (March 2020) due to the COVID-19 pandemic and schools subsequently ending in-person instruction.

The study team was unable to complete PHQ-9 screeners with two participating schools [REDACTED]. SAP outcome data will still be collected for all enrolled students (i.e., those whose parents did not return the opt-out form) for the 2019-2020 (study year 2) school year. At the completion of the year one screener/ screening process, school staff will be asked to complete the Final Feedback Guide document to assist in our research/ knowledge of the study process and procedures. Staff members from two schools completed the Feedback Guide interview [REDACTED] as a pilot to ensure the final version of the Feedback Guide was thorough and comprehensive.

At the completion of the of the 2019/2020 school year, the 3 schools that participated in the RCT during the 2018/2019 school year, will be asked to complete the Year 2 feedback guide interview document to assist in our research/knowledge of the long-term feasibility and sustainability of study processes and procedures. During their second year of study participation, school participants will be asked to complete the feedback guide interview with research personnel. Due to the COVID-19 pandemic occurring during the 2019-2020 school year, we have added questions relevant to student mental health concerns.

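### Section 8.3 opens the concern-referral route into the primary composite to the targeted arm only, although section 1.2 lists it for both arms; with unscreened students scored 0, the odds ratio can only stay equal or fall

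*Combined protocol and SAP*

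**What the plan says.** The file holds two versions of the protocol. In the current one:

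- **Section 8.3** says that the primary outcome "will be an indicator whether a student was screen positive (or concerns raised in the targeted screening arm), identified as having MDD" and then engaged in treatment, coded 1 or 0 and analysed by intention-to-treat.
- **Section 1.2, lead sentence**, has the same arm split: "MDD composite which includes MDD screen positive for the universal screening arm (or concern in the targeted screening group".
- **Section 1.2, Universal Group list**, admits students with a PHQ-9 score of 11 or more "or who at any point in the year exhibit behavior concerning for MDD prompting a SAP triage request". The Targeted Group list has the concern route alone.
- **Section 1.3** gives the universal arm both routes for the component endpoint, including students "who at any point in the school year exhibit behavior concerning for MDD which prompts self or collateral request for SAP triage".
- **Section 5.3.3.2** says that universal-arm students who decline "will not complete the PHQ-9, but will still be tracked similar to students randomized to the targeted screening arm".
- **Section 7.1** reports: "The study team was unable to complete PHQ-9 screeners with two participating schools". It adds that "SAP outcome data will still be collected for all enrolled students".

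The 8-school version has the same parenthesis in its section 8.3, "screen positive (or concerns raised in the targeted screening arm", and no arm-specific list in its section 1.2. The list is therefore new in the current version, and section 8.3 was not changed to match.

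**The concern.** The endpoint section and the statistical section define the primary variable differently. The identification and engagement steps agree; the entry step does not.

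If section 8.3 is coded as written, two kinds of universal-arm student score 0 even when they are referred, identified and engaged:

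1. students with no PHQ-9 result (no assent, form incomplete, or unscreened at the two schools in section 7.1);
2. students who score below 11 and are later referred because of concern.

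The same pathway scores 1 in the targeted arm. Detections by usual care would be counted in one arm and discarded in the other, although the protocol continues to collect them in both. At stake are a diluted estimate if screening works and, if it adds little, apparent evidence against it that comes from coding alone.

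**Working it through.** **Inputs.** Rates of 3% v 6%, two-sided 5%, 4,820 per arm (section 8.2). Attrition 15%, giving 0.85 × 4,820 = 4,097. Nine rural schools with 3,900 students and urban schools with 8,150, total 12,050 (section 8.1). The number of schools is 14 in section 1.1 but 3 + 13 = 16 in section 7.1, and 64 data points at 4 per school in section 8.3 also imply 16. Both are carried through. The average rural school has 3,900/9 = 433 students; the average urban school has 8,150/5 = 1,630 (14 schools) or 8,150/7 = 1,164 (16).

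**1. The plan's own figure.** OR = (0.06/0.94)/(0.03/0.97) = 2.064. SE of log OR = √(1/289.2 + 1/4,530.8 + 1/144.6 + 1/4,675.4) = 0.104. z = 0.7246/0.104 = 6.97, so power exceeds 99.9%, and likewise at 4,097 per arm. The stated >99% is reproduced, with students treated as independent.

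**2. Direction.** Under 8.3 with zero-coding, universal-arm events are a subset of those under the 1.2 list. Targeted-arm events and both denominators do not change, so the universal rate and the OR stay equal or fall. The planned random-intercept model was fitted under both codings to 200 simulated 14-school data sets. The log OR under 8.3 was never higher; the mean change was −0.17.

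**3. Size by share of concern-only events.** Let f be the share of universal-arm events entering by concern alone (assumed). The 8.3 rate is 0.06(1 − f). Power is for a two-proportion test at 4,820 per arm.

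| f | 8.3 rate | OR | Power |
|---|---|---|---|
| 0 | 6.0% | 2.06 | >99.9% |
| 0.10 | 5.4% | 1.85 | >99.9% |
| 0.25 | 4.5% | 1.52 | 97.2% |
| 0.40 | 3.6% | 1.21 | 37.8% |
| 0.50 | 3.0% | 1.00 | no difference left |

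**4. Size from the two schools alone.** Assume both wholly unscreened, no other non-completion, 6% in screened and 3% in unscreened universal-arm students, 3% in the targeted arm. With u the unscreened share, the 1.2 rate is 0.06(1 − u) + 0.03u and the 8.3 rate is 0.06(1 − u). If screening adds nothing, the 8.3 rate is 0.03(1 − u). False harm is the chance of a significant result against screening in that case (Wald test on log OR, 4,820 per arm).

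| Schools unscreened | u | OR, 1.2 list | OR, 8.3 | No-effect OR, 8.3 | False harm |
|---|---|---|---|---|---|
| two rural | 2 × 433.3/12,050 = 0.072 | 1.985 | 1.907 | 0.926 | 9% |
| two urban, 16 schools | 2 × 1,164.3/12,050 = 0.193 | 1.853 | 1.645 | 0.802 | 42% |
| two urban, 14 schools | 2 × 1,630/12,050 = 0.2705 | 1.769 | 1.480 | 0.723 | 70% |

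Last row in full: 8.3 rate 0.06 × 0.7295 = 0.0438, OR 1.480, SE 0.110, z = 3.57, power Φ(3.57 − 1.96) = 94.6% (90.8% at 4,097 per arm). No effect: 0.03 × 0.7295 = 0.0219, OR 0.723, SE 0.130, z = −2.50, false harm Φ(2.50 − 1.96) ≈ 70%. For two urban schools of 16, power is 99.6% (98.9% after attrition).

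**5. Partial screening.** With half of each of the two schools screened, u halves. The 8.3 OR is 1.985 to 1.769 (14 schools) or 1.985 to 1.853 (16), and false harm is 5% to 23% or 5% to 13%.

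**6. Simulation check.** 4,000 trials per case, school SD 0.4 on the logit scale (assumed), school-stratified test. With no effect and two urban schools unscreened, 67% (14 schools) and 43% (16) were significant against screening; with no school unscreened, 2.7% and 2.2%. With the universal rate twice the targeted rate, power was 89.5% and 98.4%.

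**7. If students without a PHQ-9 are dropped as missing.** The OR is 2.064, or 1.00 under no effect. If students scoring below 11 and referred later make up 0.5 or 1.0 points of the 6% (assumed), it falls to 1.882 or 1.702, because 8.3 still scores them 0.

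**The case against.** The best defence is that section 1.2 answers the question itself: its lead sentence has almost the same parenthesis as 8.3 and is then spelled out in the list, so the phrase in 8.3 can be read as shorthand for that list. Section 8.3 never says that universal-arm concerns are excluded. Continued collection of program outcomes on unscreened students would serve little purpose for the primary outcome under the narrow reading. This probably is the intent. But 8.3 specifies the analysis variable and names one arm, and a primary endpoint should not depend on which sentence the programmer follows.

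Three further points stand as limits:

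- The direction depends on zero-coding. Section 8.3 lists incomplete PHQ-9 forms under missing data without a rule for them. Dropping students without a PHQ-9 departs from intention-to-treat and, if no events come from later referral after a score below 11, gives an OR of 2.064, above the 1.985 to 1.769 of the 1.2 list.
- The false-harm figures are illustrations. The 70% needs 14 schools, two average urban schools wholly unscreened, no true effect and independent students. After 15% attrition it is 63% (36% rather than 42% with 16 schools). An assumed design effect of 1.5 for assignment by grade brings 70% to 53%. In the other direction, these figures assume that all events in screened students enter through a positive PHQ-9; any concern-only events among them would lower the OR further.
- At the planned effect, the two-school scenario still leaves power of about 90% or more.

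**Conclusion.** The concern holds. The current text gives two definitions of the primary composite, and the one in the statistical section is biased against the universal arm if followed under intention-to-treat with a 1/0 indicator. That conclusion rests on the wording and a subset argument, and confidence in it is high.

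The size is not known, because the documents give neither the number of universal-arm students without a PHQ-9 nor the share of events that enter by concern alone. Under the assumptions shown, the main harm at 3% v 6% is an attenuated odds ratio rather than lost power. A substantial loss of power needs a large concern-only share, around 40% of universal-arm events. If screening adds little or nothing, the coding could by itself produce a significant result against it. This should be corrected before analysis.

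**What to change.** Replace the composite definition in section 8.3 and the lead sentence of section 1.2 with the arm-specific list already in 1.2:

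- universal arm: PHQ-9 score of 11 or more, or a concern-prompted triage request to the Student Assistance Program at any point in the school year;
- targeted arm: a concern-prompted triage request;
- both arms: followed by identification and engagement.

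Add one line that universal-arm students without a PHQ-9 stay in the analysis and are scored through the concern route. The separately analysed secondary outcomes in 8.3 can stay as they are.

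The cost is one sentence in 8.3, one in 1.2 and the added line. No new data are needed: sections 7.1 and 7.2.1 already provide for program outcomes on all enrolled students in both arms.
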